7.2.4.1. Dose Delays for Adverse Events

Study treatment may be held for a maximum of 28 days; see exception for an immune-related AE below. If appropriate, and in the opinion of the investigator and upon agreement with the sponsor, study treatment may resume upon resolution of clinically significant AEs to baseline or improvement to Grade <2. If AEs, see exception for an immune-related AE, do not resolve to baseline or improve to Grade <2 within 28 days following the last administered dose, study treatment should be permanently discontinued and the patient should be discontinued from the trial. If treatment is held, the day of treatment should continue as if no drug interruption has occurred. For example, if study drug is held on D6 of a cycle and AEs have resolved by D10 (4 days later), the study drugs should be resumed per the original schedule. If the original schedule results in a study drug being held for >28 days, the study drug may not be resumed. One or both study drugs may be held, resumed, or discontinued.

If the AE is an immune related AE as outlined in [Attachment 7](#), and if the treatment management guidelines outlined in [Attachment 7](#) are followed and documented in the patient's medical record, treatment may be held for >28 days to allow taper of high dose steroids. Treatment may resume in this setting only upon resolution of immune AEs to baseline or improvement to Grade <2, and only if deemed clinically appropriate by the treating physician and agreed to by the sponsor. If steroids cannot be tapered as outlined in [Attachment 7](#), and/or AEs do not resolve to < Grade 2, the patient may not be resumed on study treatment.

For the purposes of documentation, the investigator must assess if the toxicity is considered at least possibly related to study treatment (that is, the combination regimen) and if the AE is considered to be immune related. Investigators are encouraged to consult the sponsor for additional guidance.

For AEs that are considered at least possibly related to study treatment, the following dose adjustment guidance may be applied:

- Treat each of the toxicities with maximum supportive care (including holding the study drug[s] suspected of causing the toxicity where required).
- If the symptoms promptly resolve with supportive care, consideration should be given to continuing the same dose of study drugs along with appropriate continuing supportive care.

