- All dose modifications should be documented with clear reasoning and documentation of the approach taken.

In addition, there are certain circumstances in which study drugs should be permanently discontinued (refer to [Attachment 7](#)).

Following the first dose of study drugs, subsequent administration of study drugs can be modified based on toxicities observed (refer to [Attachment 7](#)).

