Grade 3 or 4	
For Grade 3 or 4: Permanently discontinue study drug/study regimen.
	
For Grade 3 or 4:
 
 – Manage severe infusion-related reactions per institutional standards (eg, IM epinephrine, followed by IV diphenhydramine and ranitidine, and IV glucocorticoid).

Abbreviations: CTCAE = Common Terminology Criteria for Adverse Events; IM = intramuscular; IV = intravenous; NCI = National Cancer Institute.

Non-Immune-Mediated Reactions

Severity Grade of the Event (NCI CTCAE version 4.03)	Dose Modifications	Toxicity Management
Any Grade	Note: Dose modifications are not required for AEs not deemed to be related to study treatment (ie, events due to underlying disease) or for laboratory abnormalities not deemed to be clinically significant.	Treat accordingly, as per institutional standard.
Grade 1	No dose modifications.	Treat accordingly, as per institutional standard.
Grade 2	Hold study drug/study regimen until resolution to \leq Grade 1 or baseline. For asymptomatic Grade 2 creatine kinase levels:	Treat accordingly, as per institutional standard. For asymptomatic Grade 2 creatine kinase levels:
	
 Hold treatment with both study agents. Perform diagnostic evaluation 
If results show no evidence of end organ damage, including myositis and rhabdomyolysis, resume treatment with both agents.
	
 Perform diagnostic evaluation (serum and urine myoglobin, BUN and creatinine) 
Continue to monitor CK, serum and urine myoglobin, BUN and creatinine Weekly until creatine kinase levels return to \leq Grade 1 or as clinically indicated.

Grade 3	Hold study drug/study regimen until resolution to \leq Grade 1 or baseline. For AEs that downgrade to \leq Grade 2 within 7 days or resolve to \leq Grade 1 or baseline within 14 days, resume study drug/study regimen administration. Otherwise, discontinue study drug/study regimen. For asymptomatic Grade 3 creatine kinase levels:	Treat accordingly, as per institutional standard.

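### Restart after a Grade 3 non-immune adverse event that settles at Grade 2: Attachment 7 contradicts itself and Section 7.2.4.1, and no text says which governs

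*Protocol*

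**What the plan says.** Two places in the current protocol text govern restart after a Grade 3 non-immune event.

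- **Attachment 7, Non-Immune-Mediated Reactions, Grade 3 row.** The join between the first two sentences of the cell reads "Grade 1 or baseline. For AEs that downgrade to". The first sentence holds treatment to Grade 1 or lower, or baseline. The second opens two routes back: Grade 2 or lower inside a week ("Grade 2 within 7 days or resolve to"), or Grade 1 or lower, or baseline, "within 14 days, resume study drug/study regimen administration. Otherwise, discontinue study drug/study regimen".
- **Section 7.2.4.1, Dose Delays for Adverse Events.** The ceiling is "Study treatment may be held for a maximum of 28 days; see exception for an immune-related AE below". Within it, "study treatment may resume upon resolution of clinically significant AEs to baseline or improvement to Grade <2", if the investigator thinks it appropriate and the sponsor agrees. If that level is not reached "within 28 days following the last administered dose, study treatment should be permanently discontinued". The only exception is for immune-related events, where a steroid taper may run past 28 days.

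Section 7.2.4.1 closes with two pointers to Attachment 7. One is for circumstances that call for permanent discontinuation. The other says that "subsequent administration of study drugs can be modified based on toxicities observed". Neither gives an order of precedence for non-immune events.

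The same Attachment 7 table exempts events not deemed related to treatment and laboratory changes not deemed clinically significant. It also gives asymptomatic Grade 3 creatine kinase elevation its own steps.

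**The concern.** A site facing a non-immune Grade 3 event that eases to Grade 2 and stays there has one sentence telling it to restart and two that do not allow it. A patient could be re-dosed at a grade that another part of the protocol does not accept. Whichever sentence the site follows, its action can be classed as a deviation from another.

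Safety and tolerability are a primary objective (Protocol 5.2.1). The SAP reports reasons for treatment discontinuation (6.4), and dose adjustments and dose intensity (6.8.1). Each of these depends on which sentence is followed. Amendment (c) set out to make the delay criteria consistent (5.1.3), and this row was left unreconciled.

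**Working it through.** No sample size, power or event count bears on this point. The check applies each rule to the same hypothetical courses.

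**Inputs**
- Attachment 7, second sentence of the cell: restart if Grade ≤2 within 7 days, or Grade ≤1 or baseline within 14 days; otherwise stop.
- Section 7.2.4.1: restart allowed at baseline or Grade <2; stop if not reached within 28 days of the last administered dose.
- Lag from last dose to onset, with dosing on schedule: 0 to 6 days for weekly dosing, and 0 to 13 days where doses are 14 days apart (from the dosing-day definitions under Table JSCC.1).

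**Assumptions.** The event is related and clinically significant, and baseline is below Grade 2. Attachment 7's 7- and 14-day limits are taken to run from onset, because the protocol gives no start point.

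**Formulas**
- Latest day after onset for recovery under 7.2.4.1 = 28 − lag. For lags of 0, 6 and 13 days this is day 28, 22 and 15.
- Width of the window in which Attachment 7 stops but 7.2.4.1 may allow restart = (28 − lag) − 14 = 14 − lag. For the same lags this is 14, 8 and 1 days.

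| Course after Grade 3 onset | Attachment 7, second sentence | Section 7.2.4.1 |
|---|---|---|
| Grade 2 on day 5, Grade 1 on day 10 | restart | may restart |
| Grade 2 on day 5, never lower | restart | hold, then stop at day 28, 22 or 15 (lag 0, 6, 13) |
| Grade 2 on day 5, Grade 1 on day 18 | restart | may restart (lag 0 or 6); stop (lag 13, since 18 + 13 = 31 > 28) |
| Grade 2 on day 10, Grade 1 on day 12 | restart | may restart |
| Grade 2 on day 10, Grade 1 on day 18 | stop | may restart (lag 0 or 6); stop (lag 13) |
| Grade 2 on day 10, never lower | stop | hold, then stop |
| Never down to Grade 2 | stop | hold, then stop |

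**Main conflict (second course).** Attachment 7's second sentence restarts. Its first sentence holds, since Grade 1 or baseline is never reached. Section 7.2.4.1 holds and then stops. The Grade 2 row of the same Attachment 7 table also holds a Grade 2 event until Grade 1 or lower, or baseline.

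**Secondary ambiguity (fifth course).** Attachment 7 stops. Section 7.2.4.1 may allow restart, depending on the lag. The event must still be above Grade 2 at day 7; otherwise the 7-day route in Attachment 7 applies and the patient restarts.

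**The case against.** There are three fair points on the other side.

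1. **The second sentence of the cell may refine the first.** On that reading, treatment is held to Grade 1 unless the event drops to Grade 2 quickly. The cell does not say so. Even if it did, restart at a persistent Grade 2 would still conflict with 7.2.4.1, which accepts only baseline or below Grade 2. The main conflict stands.
2. **Section 7.2.4.1 is permissive and points to Attachment 7 for further stopping circumstances.** A 14-day stop can then sit as a stricter specific rule inside a 28-day ceiling. That is a reasonable reading of the secondary case, which is why it is called an ambiguity here. No text states it, and the two clocks do not match: one runs from the last dose and the other has no stated start. The reading does not help the main case, where Attachment 7 is the looser text on grade.
3. **Sponsor agreement is needed to restart under 7.2.4.1**, which limits independent variation between sites. It does not tell the sponsor which text to apply, and the Grade 3 sentence in Attachment 7 carries no such condition.

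A reader might also infer that evaluability for dose-limiting toxicity is broadly at stake. The documents support only a limited version. Section 7.2.2.1 counts many Grade 3 non-immune events in Cycle 1 as dose-limiting, subject to its exclusions and its general improvement clause. Under 7.6.1, a patient with such an event before withdrawal is not made nonevaluable. The link remains for Grade 3 events outside that definition, such as fatigue of 7 days or less. The evaluability concept does not apply in Part B.

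**Conclusion.** Wrong as written, for a defined course: a treatment-related, clinically significant Grade 3 non-immune event, other than asymptomatic creatine kinase elevation, in a patient with baseline below Grade 2, that falls to Grade 2 within 7 days and stays there. For events still above Grade 2 at day 7 that reach Grade 1 after day 14 but within 28 days of the last dose, the text is ambiguous. With Attachment 7's limits counted from onset, that window is 8 to 14 days for weekly dosing and 1 to 14 days where doses are 14 days apart.

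Three stronger readings are tempting and are not supported:

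- **That the rules are opposite for every Grade 3 non-immune event.** Several courses in the table end the same way. The related-and-clinically-significant condition, the creatine kinase rule and a Grade 2 baseline remove others. Because held dosing resumes on the original schedule, an event that reaches Grade 1 before the next scheduled dose is also unaffected.
- **That the conflict spans half of the 28-day allowance.** Fourteen days is the upper bound, reached only at zero lag.
- **That the Part B discontinuation rate could move by a given amount.** Assuming 4 affected patients of 40 would give 4/40 = 10 percentage points, but no document supports the 4. The two groups also move in opposite directions: Attachment 7 keeps the first and stops the second, while 7.2.4.1 eventually stops the first and may keep the second. A 2 + 2 split would net to zero. With no frequency in the documents, no rate effect can be stated.

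**What to change.** Reconcile Section 7.2.4.1 with the Grade 3 row of the Attachment 7 non-immune table so that the resumption grade, the time limits and the point from which each limit is counted agree. Make the sentences within that cell consistent with each other. Add a statement of which text governs non-immune events, as 7.2.4.1 already ties immune-related events to Attachment 7. A tiered rule or a single rule would each serve, provided it reads the same in both places. Which clinical rule to adopt, and which text to change, is for the sponsor.

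The cost is an amendment to one table cell and one sentence on precedence, with no added patients, visits or procedures.

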7.2.1.1. LY3022855

Eligible patients will receive LY3022855 as an I.V. infusion administered over a minimum duration of 30 minutes and a maximum duration of 4 hours, based on the known safety and stability of the prepared drug. The infusion rate should not exceed 25 mg/minute. Suggested infusion times are as follows:

- 90 minutes for the first infusion; if no infusion-related reaction (IRR) is observed, decrease the infusion time to 60 minutes for the second infusion
- 60 minutes for the second infusion; if no IRR is observed, decrease the infusion time to 30 minutes for the third infusion
- 30 minutes for the third and subsequent infusions

If, at any time, a patient experiences an IRR, the infusion time should not be decreased.

Premedication is not recommended to be administered prior to the first infusion of LY3022855. However, if the patient experiences a Grade 1 or 2 IRR, premedication must be provided prior to any subsequent doses of LY3022855. The choice of premedication is to be made after discussion and agreement between the investigator and sponsor. In such cases (Grade 1 or 2 IRRs), administration of steroids should be avoided, if possible. If an IRR Grade ≤ 2 occurs during or after LY3022855 administration and the patient's condition allows it, treatment with durvalumab or tremelimumab will proceed as planned. Patients experiencing an IRR Grade ≥ 3 will be permanently discontinued from study treatment.

LY3022855 may be administered up to 3 days AFTER the scheduled dosing date and up to 4 days BEFORE the next scheduled dosing date to accommodate for patient vacations, holidays, inclement weather or other unforeseen circumstances. If, at any time, a dose is to be administered beyond the 3-day window, that dose is to be skipped. A maximum of 28 days between administered doses is allowed for delays due to adverse events.

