
may be permanently discontinued. Please refer to guidelines below.
 
Grade 4 Permanently discontinue study drug/study regimen.
 
Note: For Grade ≥ 3 asymptomatic amylase or lipase levels, hold study drug/study regimen, and if complete work up shows no evidence of pancreatitis, study drug/study regimen may be continued or resumed.
 
Note: Study drug/study regimen should be permanently discontinued in Grade 3 events with high likelihood for morbidity and/or mortality – e.g., myocarditis, or other similar events even if they are not currently noted in the guidelines.
 
Similarly, consider whether study drug/study regimen should be permanently discontinued in Grade 2 events with high likelihood for morbidity and/or mortality – e.g., myocarditis, or other similar events even if they are not currently noted in the guidelines – when they do not rapidly improve to Grade <1 upon treatment with systemic steroids and following full taper.
 
Note: There are some exceptions to permanent discontinuation of study drug for Grade 4 events (i.e., hyperthyroidism, hypothyroidism, Type 1 diabetes mellitus).
	
guidelines – when these events are not responding to systemic steroids.
 
 – With long-term steroid and other immunosuppressive use, consider need for Pneumocystis jirovecii pneumonia (PJP, formerly known as Pneumocystis carinii pneumonia) prophylaxis, gastrointestinal protection, and glucose monitoring. – Discontinuation of study drug/study regimen is not mandated for Grade 3/Grade 4 inflammatory reactions attributed to local tumor response (e.g., inflammatory reaction at sites of metastatic disease and lymph nodes). Continuation of study drug/study regimen in this situation should be based upon a benefit/risk analysis for that patient.

Abbreviations: AE = Adverse event; CTC = Common Toxicity Criteria; CTCAE = Common Terminology Criteria for Adverse Events; imAE = immune-mediated adverse event; IV = intravenous; NCI = National Cancer Institute; PO = By mouth.

Specific Immune-Mediated Reactions			
Adverse Events	Severity Grade of the Event (NCI CTCAE version 4.03)	Dose Modifications	Toxicity Management

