	Grade 3 or 4	
For Grade 3 or 4 endocrinopathy other than hypothyroidism and Type 1 diabetes mellitus, hold study drug/study regimen dose until endocrinopathy symptom(s) are controlled.
 
Study drug/study regimen can be resumed once event stabilizes and after completion of steroid taper.
 
Patients with endocrinopathies who may require prolonged or continued steroid replacement (e.g., adrenal insufficiency) can be retreated with study drug/study regimen on the following conditions:
 
 1. The event stabilizes and is controlled. 2. The patient is clinically stable as per investigator or treating physician's clinical judgment. 3. Doses of prednisone are ≤ 10 mg/day or equivalent. 	
For Grade 3 or 4:
 
Consult endocrinologist to guide evaluation of endocrine function and, as indicated by suspected endocrinopathy and as clinically indicated, consider pituitary scan. Hospitalization recommended.
 
 For all patients with abnormal endocrine workup, except those with isolated hypothyroidism or Type 1 DM, and as guided by an endocrinologist, promptly initiate empiric IV methylprednisolone 1 to 2 mg/kg/day or equivalent, as well as relevant hormone replacement (e.g., hydrocortisone, sex hormones). For adrenal crisis, severe dehydration, hypotension, or shock, immediately initiate IV corticosteroids with mineralocorticoid activity. Isolated hypothyroidism may be treated with replacement therapy, without study drug/study regimen interruption, and without corticosteroids. Isolated Type 1 diabetes mellitus may be treated with appropriate diabetic therapy, without study drug/study regimen interruption, and without corticosteroids. Once patients on steroids are improving, gradually taper immunosuppressive steroids (as appropriate and with guidance of endocrinologist) over ≥ 28 days and consider prophylactic antibiotics, antifungals, and anti-PJP treatment (refer to current NCCN guidelines for treatment of cancer-related infections [Category 2B recommendation]).^a

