	
Grade 2 (moderate pain associated with weakness; pain limiting instrumental activities of daily living [ADLs])
	
 - Hold study drug/study regimen dose until resolution to Grade ≤ 1. - Permanently discontinue study drug/study regimen if it does not resolve to Grade ≤ 1 within 30 days or if there are signs of respiratory insufficiency. 	
For Grade 2:
 
 - Monitor symptoms daily and consider hospitalization. - Obtain Neurology consult, and initiate evaluation. - Consider, as necessary, discussing with the study physician. - If clinical course is rapidly progressive (particularly if difficulty breathing and/or trouble swallowing), promptly start IV methylprednisolone 2 to 4 mg/kg/day systemic steroids along with receiving input from Neurology consultant. - If clinical course is not rapidly progressive, start systemic steroids (eg, prednisone 1 to 2 mg/kg/day PO or IV equivalent); if no improvement within 3 to 5 days, continue additional work up and start treatment with IV methylprednisolone 2 to 4 mg/kg/day. - If after start of IV methylprednisolone at 2 to 4 mg/kg/day there is no improvement within 3 to 5 days, consider start of immunosuppressive therapy such as TNF inhibitors (eg, infliximab at 5 mg/kg every 2 weeks). Caution: It is important to rule out sepsis and refer to infliximab label for general guidance before using infliximab. - Once the patient is improving, gradually taper steroids over ≥ 28 days and consider prophylactic antibiotics, antifungals, or anti-

			PJP treatment (refer to current NCCN guidelines for treatment of cancer-related infections [Category 2B recommendation]). ^a

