	
Grade 3 or 4 (pain associated with severe weakness; limiting self-care ADLs)
 
For Grade 3: Hold study drug/study regimen dose until resolution to Grade ≤ 1. Permanently discontinue study drug/study regimen if Grade 3 imAE does not resolve to Grade ≤ 1 within 30 days or if there are signs of respiratory insufficiency.
 
For Grade 4: - Permanently discontinue study drug/study regimen.
	
For Grade 3 or 4 (severe or life-threatening events):
 
 - Monitor symptoms closely; recommend hospitalization. - Obtain Neurology consult, and complete full evaluation. - Consider, as necessary, discussing with the study physician. - Promptly start IV methylprednisolone 2 to 4 mg/kg/day systemic steroids along with receiving input from Neurology consultant. - If after start of IV methylprednisolone at 2 to 4 mg/kg/day there is no improvement within 3 to 5 days, consider start of immunosuppressive therapy such as TNF inhibitors (eg, infliximab at 5 mg/kg every 2 weeks). Caution: It is important to rule out sepsis and refer to infliximab label for general guidance before using infliximab. - Consider whether patient may require IV IG, plasmapheresis. - Once the patient is improving, gradually taper steroids over ≥ 28 days and consider prophylactic antibiotics, antifungals, or anti-PJP treatment (refer to current NCCN guidelines for treatment of cancer-related infections [Category 2B recommendation]).^a 	

^a ASCO Educational Book 2015 “Managing Immune Checkpoint Blocking Antibody Side Effects” by Michael Postow MD.

^b FDA Liver Guidance Document 2009 Guidance for Industry: Drug Induced Liver Injury – Premarketing Clinical Evaluation.

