Abbreviations: AChE = Acetylcholine esterase; ADL = Activities of daily living; AE = Adverse event; ALP = Alkaline phosphatase test; ALT = Alanine aminotransferase; AST = Aspartate aminotransferase; BUN = Blood urea nitrogen; CT = Computed tomography; CTCAE = Common Terminology Criteria for Adverse Events; HbA1C = glycated haemoglobin; ILD = Interstitial lung disease; imAE = immune-mediated adverse event; IG = Immunoglobulin; IV = Intravenous; GI = Gastrointestinal; LFT = Liver function tests; LLN = Lower limit of normal; MRI = Magnetic resonance imaging; NCI = National Cancer Institute; NCCN = National Comprehensive Cancer Network; PJP = Pneumocystis jirovecii pneumonia (formerly known as Pneumocystis carinii pneumonia); PO = By mouth; T3 = Triiodothyronine; T4 = Thyroxine; TB = Total bilirubin; TNF = Tumor necrosis factor; TSH = Thyroid-stimulating hormone; ULN = Upper limit of normal.

Infusion-Related Reactions

Severity Grade of the Event (NCI CTCAE version 4.03)	Dose Modifications	Toxicity Management
Any Grade	General Guidance	
For Any Grade:
 
 – Manage per institutional standard at the discretion of investigator. – Monitor patients for signs and symptoms of infusion-related reactions (eg, fever and/or shaking chills, flushing and/or itching, alterations in heart rate and blood pressure, dyspnea or chest discomfort, or skin rashes) and anaphylaxis (eg, generalized urticaria, angioedema, wheezing, hypotension, or tachycardia).
Grade 1 or 2	
For Grade 1: The infusion rate of study drug/study regimen may be decreased by 50% or temporarily interrupted until resolution of the event.
 
For Grade 2: The infusion rate of study drug/study regimen may be decreased 50% or temporarily interrupted until resolution of the event. Subsequent infusions may be given at 50% of the initial infusion rate.
	
For Grade 1 or 2:
 
 – Acetaminophen and/or antihistamines may be administered per institutional standard at the discretion of the investigator. – Consider premedication per institutional standard prior to subsequent doses. – Steroids should not be used for routine premedication of Grade ≤ 2 infusion reactions.

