	
Hold treatment with both LY3022855 and durvalumab or tremelimumab. Perform diagnostic evaluation.
 
 For Grade 3 elevations in CK \leq 8X ULN with a diagnostic evaluation showing NO evidence of end organ damage including myositis or rhabdomyolysis, resume treatment with both agents. For Grade 3 elevations in CK $>$ 8X ULN with a diagnostic evaluation showing NO evidence of end organ damage including myositis or rhabdomyolysis, hold LY3022855 and resume durvalumab or 	
 Perform diagnostic evaluation (serum and urine myoglobin, BUN and creatinine). Continue to monitor CK, serum and urine myoglobin, BUN and creatinine Weekly until CK levels return to \leq Grade 1 or as clinically indicated. Treat accordingly as per institutional standard, perform a full diagnostic evaluation and if there is any evidence of potential immune-mediated end organ damage, follow the guidelines for irAE management contained in this attachment.

Non-Immune-Mediated Reactions

Severity Grade of the Event (NCI CTCAE version 4.03)	Dose Modifications	Toxicity Management
	
tremelimumab after discussion with sponsor.
 
If CK decreases to $\leq 8x$ ULN after holding LY3022855, resume treatment with LY3022855 and durvalumab or tremelimumab.
 
 ○ If CK remains $>8X$ ULN after holding LY3022855, permanently discontinue both LY3022855 and durvalumab or tremelimumab and discuss additional treatment measures with sponsor. 
In case of myositis or rhabdomyolysis, permanently discontinue treatment with both study agents.
	
 ● Continue to monitor CK, serum and urine myoglobin, BUN and creatinine weekly until CK levels return to \leq Grade 1 or baseline.
Grade 4	
Discontinue study drug/study regimen (Note: For Grade 4 labs, decision to discontinue should be based on accompanying clinical signs/symptoms, the Investigator's clinical judgment, and consultation with the Sponsor.).
	Treat accordingly, as per institutional standard.

Note: As applicable, for early phase studies, the following sentence may be added: "Any event greater than or equal to Grade 2, please discuss with Study Physician."

Abbreviations: AE = Adverse event; BUN = elevated serum blood urea nitrogen; CK = creatinine; CTCAE = Common Terminology Criteria for Adverse Events;

NCI = National Cancer Institute.

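### Attachment 7 gives incompatible stopping instructions for myositis found on a Grade 3 CK work-up and for Grade 4 endocrinopathies outside its three named exceptions

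*Protocol*

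**What the plan says.** All of this is current text in Attachment 7 of the protocol.

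**Myositis**
- *Non-Immune-Mediated Reactions, Grade 3, asymptomatic CK, dose-modification column:* "In case of myositis or rhabdomyolysis, permanently discontinue treatment with both study agents". No myositis grade is given and no route back to treatment is described.
- *Same row, management column:* "if there is any evidence of potential immune-mediated end organ damage, follow the guidelines for irAE management contained in this attachment".
- *Myositis/Polymyositis row, Grade 1 (mild pain):* no dose modification.
- *Myositis/Polymyositis row, Grade 2:* hold until Grade 1 or lower. "Permanently discontinue study drug/study regimen if it does not resolve to Grade" 1 or lower within 30 days, or if there are signs of respiratory insufficiency.
- *Myositis/Polymyositis row, Grade 3:* the same pattern. "Permanently discontinue study drug/study regimen if Grade 3 imAE does not resolve to Grade" 1 or lower within 30 days, or with respiratory signs.
- *Myositis/Polymyositis row, Grade 4:* permanent discontinuation.

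**Grade 4 endocrinopathy**
- *General Considerations:* Grade 4 means permanent discontinuation, with this note: "There are some exceptions to permanent discontinuation of study drug for Grade 4 events (i.e., hyperthyroidism, hypothyroidism, Type 1 diabetes mellitus").
- *Endocrinopathy row:* "For Grade 3 or 4 endocrinopathy other than hypothyroidism and Type 1 diabetes mellitus, hold study drug/study regimen dose until endocrinopathy symptom(s) are controlled". Treatment may resume once the event is stable and the steroid taper is complete. Patients who need continued steroid replacement, with adrenal insufficiency as the example, may be retreated under three listed conditions.

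**The concern.** A site must be able to read one instruction for one event. Here a patient with Grade 3 CK and mild myositis is to be taken off both drugs for good under one column. Under the table to which the neighbouring column refers, the same patient continues or is held. A patient with Grade 4 adrenal insufficiency meets the same problem between the general rule and the endocrine row.

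The first stake is patient safety, since these are stop-or-continue instructions. The second is what the trial reports. Safety and tolerability form a primary objective (protocol 5.2.1). The SAP tabulates reasons for discontinuing treatment (6.4) and cycles received, duration on therapy, cumulative dose and dose intensity by cohort (6.8.1). For the affected patients, these summaries would partly reflect which row a site followed, not how the regimen was tolerated.

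**Working it through.** The plan gives no figure to reproduce. The check is a comparison of the current rows, event by event.

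**Step 1. Can one patient fall under both myositis instructions?** Yes.
- The grade in the CK row is the laboratory grade (5-10 times the upper limit of normal in protocol 7.2.2.1). Myositis is graded by pain and weakness. A Grade 3 CK can therefore accompany a low-grade myositis.
- Protocol 7.2.2.1 exempts asymptomatic Grade 3 CK from being a DLT only if there is no evidence of rhabdomyolysis or myositis. The protocol thus foresees that this work-up may find myositis.
- General Considerations say that events without a clear alternative cause are to be managed as immune related. Protocol 7.2.4.1.1 applies the same default to myopathy.
- The initial work-up in the myositis row includes CK and urine myoglobin, which overlaps the CK evaluation.

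**Step 2. Myositis, grade by grade**

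| Finding on Grade 3 CK work-up | CK row | Myositis row | Conflict |
|---|---|---|---|
| Myositis Grade 1 | Permanent stop, both drugs | No dose modification | Yes |
| Grade 2-3, resolves to Grade 1 or lower within 30 days, no respiratory signs | Permanent stop, both drugs | Hold until resolved | Yes |
| Grade 2-3, unresolved at 30 days or respiratory signs | Permanent stop | Permanent stop | No |
| Grade 4 | Permanent stop | Permanent stop | No |
| Rhabdomyolysis | Permanent stop | Not addressed | No |

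For Grades 2-3 the myositis row does not itself say to resume. Restart is implied by holding until resolution, and protocol 7.2.4.1 permits it.

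**Step 3. Grade 4 endocrinopathy**

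| Grade 4 event | General Considerations | Endocrine row | Conflict |
|---|---|---|---|
| Isolated hypothyroidism or Type 1 diabetes | Excepted from permanent stop | Treat without interruption | No |
| Hyperthyroidism | Excepted from permanent stop | Hold, then resume | No |
| Adrenal insufficiency, hypophysitis, hypopituitarism | Permanent stop | Hold, then resume or retreat | Yes |

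The exceptions are introduced by *i.e.*, which makes the list closed.

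**Step 4. Size**
- Protocol 5.1.2 reports CK rises in 17 of 64 monotherapy patients (17/64 = 26.6%), mostly at Grades 1 and 2. The permanent-stop sentence is in the Grade 3 CK text only, and myositis must also be found. The rate of the conflict is therefore not 26.6%, and the documents give no figure from which to compute it. They report one Grade 4 rhabdomyolysis with LY3022855, which is not in conflict, and no myositis.
- The documents give no rate for Grade 4 endocrinopathy.
- In a 20-patient Part B cohort, one patient handled differently moves the discontinuation rate by 1/20 = 5 percentage points. This is the weight of one patient and says nothing about how often the case will occur.

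**The case against.** The strongest defence of the myositis text is that the two rows serve different patients. The CK text is headed non-immune-mediated and asymptomatic, whereas the myositis rows are immune-mediated and graded by symptoms. On this view, the reference to the immune-related guidelines is a routing rule: once organ damage looks immune-mediated, the site leaves the CK row. Restart is also not left to the site alone, because protocol 7.2.4.1 requires the sponsor's agreement.

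Much of this stands. It narrows the overlap, and the sponsor's agreement is a real safeguard against inconsistent restarts. It does not remove the conflict. The stop sentence names myositis without restricting it to non-immune cases or to any grade, and it stands in the row that does the routing. Neither text says which governs. Patients with few symptoms are the likeliest to come through an asymptomatic CK row, and they lie nearest Grade 1 myositis, where the two instructions differ most. The sponsor's agreement also does not settle the Grade 1 case, where the question is whether to stop at all.

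For endocrinopathy, the defence is that a specific row overrides a general rule, and that the general rule itself admits exceptions. That is a reasonable reading, but Attachment 7 does not state it, and a closed list of exceptions points the other way.

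**Conclusion.** Attachment 7 contradicts itself on stopping treatment in two places: Grade 1 or resolving Grade 2-3 myositis found on a Grade 3 CK work-up, and Grade 4 endocrinopathies other than hyperthyroidism, hypothyroidism and Type 1 diabetes. The first should be uncommon; the frequency of the second is unknown. The conclusion rests on the rows as written and on the absence of a stated precedence.

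A reader might infer more than the documents support:
- *That about a quarter of patients will meet the conflict.* The 17 of 64 are CK rises of any grade. The 19 of 64 with AST rises have no bearing on a myositis rule.
- *That myositis is an observed LY3022855 signal.* The reported signal is enzyme elevation, with one case of rhabdomyolysis.
- *That DLET counts are affected.* DLT and DLET status follows the criteria in protocol 7.2.2.1, whichever Attachment 7 row is used.
- *That premedication after a Grade 1-2 infusion reaction is a third contradiction.* Protocol 7.2.1.1 says "premedication must be provided prior to any subsequent doses of LY3022855", and Attachment 7 says "Consider premedication per institutional standard prior to subsequent doses". A site that follows the first also satisfies the second. The Attachment 7 wording covers all study drugs, and protocol 7.5.2 refers sites to 7.2.1.1 for premedication.

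**What to change.** Reconcile each pair so that one instruction governs each event:
1. In the Grade 3 CK row, state which table prevails when the work-up shows myositis, and make the stop sentence and the reference to the immune-related guidelines agree. The Grade 2 CK text does not say what follows if myositis is found, so the same edit could cover it.
2. Make the Grade 4 exception list in General Considerations and the Grade 3 or 4 endocrine row agree, or state that event-specific rows override the general rule.

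Which version stands is for the sponsor's medical team to decide. The cost is Attachment 7 wording in the next amendment and a site memo until then. Sample size, data collection and the analysis plan do not change.
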